8.15. Missed Assessments

Missed assessments should be rescheduled and performed as close to the originally scheduled date as possible. An exception is made when rescheduling becomes, in the Investigator's opinion, medically unnecessary or unsafe because it is too close in time to the next scheduled evaluation. In that case, the missed evaluation should be abandoned.

8.16. End of Study Visit

The EOS is defined as the visit that occurs 28 days after the last dose of study drug. Assessments for this visit are outlined in the Schedule of Assessments ([Appendix A](#), [Appendix B](#)).

If the participant terminates study drug early, every effort should be made to collect the Day 168/End-of-Treatment assessments. The participant should also be asked to attend the Safety Follow-up visit 28 days later.

8.17. Participant Discontinuation from the Study

The reasons for a participant's discontinuation from the study may include but are not limited to the following:

- Patient withdrawal of consent
- Study termination
- Adverse event
- Loss to follow-up
- Participant non-compliance, defined as failure to comply with protocol requirements, as determined by the Investigator or Sponsor

If a participant requests to be withdrawn from the study, this information should be documented and signed by the Investigator. No further data will be collected from the signed date onwards.

8.18. Order of Assessments

Visits should take place in the morning. Participants are instructed to hold study drug until a predose blood sample for PK is obtained at the investigational site.

For procedures scheduled to be performed at the same timepoint, the order of assessments is as follows: vital signs, PK sample collection, blood draw for PD/safety laboratory assessments, ECGs. If times are delayed due to technical difficulties, this will be noted but not considered a protocol violation.

The predose PK sample should be collected within 30 min prior to dosing.

On Day 1 in Period 1:

- Triplicate ECGs should be recorded at 3 timepoints prior to dosing (-45 min, -30 min, -15 min).
- Postdose triplicate ECGs (after the morning dose) should be recorded within 15 min following the 2-hour PK sample collection.

On Day 1 in Periods 2, 3, and 4, on Day 7 in all periods, and on Day 21 in Period 4:

- Predose triplicate ECGs should be recorded within 15 min following the predose PK sample collection.
- Postdose triplicate ECGs (after the morning dose) should be recorded within 15 min following the 2-hour PK sample collection.

All PD assessments should be performed after the PK assessments. RBC deformability and dense cells will be tested, if feasible, by the local or collaborating lab at the time of collection.

9. ADVERSE AND SERIOUS ADVERSE EVENTS

Safety assessments will consist of recording all AEs and SAEs, protocol-specified hematology and clinical chemistry variables, clinical examination findings, measurement of protocol-specified vital signs, and the results from other protocol-specified tests that are deemed critical to the safety evaluation of voxelotor.

The determination, evaluation, reporting, and follow-up of AEs will be performed as outlined in Section 9.1. At each visit, the study participant or participant caregiver will be asked about any new or ongoing AE since the previous visit. Assessments of AEs will occur at each study visit. See Section 9.2 for details regarding the required time periods for AE reporting.

Clinically significant changes from study baseline in physical examination findings, weight, vital signs, and clinical laboratory parameters will be recorded as AEs or SAEs, as appropriate.

9.1. Adverse Events

9.1.1. Definition of Adverse Events

An AE is defined as any untoward medical occurrence associated with the use of a drug in humans, whether or not considered drug related. An AE can therefore be any unfavorable and unintended sign, symptom, or disease temporally associated with the use of an investigational product, whether or not thought to be related to the investigational product. An AE may also constitute complications occurring as a result of protocol-mandated interventions (eg, invasive procedures such as biopsies), including the period prior to receiving the first dose of the study drug (eg, medication wash out). In addition to new events, any increase in the severity or frequency of a pre-existing condition that occurs after the participant signs the ICF is considered an AE. This includes any side effect, injury, toxicity, or sensitivity reaction.

A suspected adverse reaction is any AE for which there is a reasonable possibility that the drug caused the AE. For the purposes of expedited safety reporting, “Reasonable possibility” means there is evidence to suggest a causal relationship between the drug and the AE. Suspected adverse reaction implies a lesser degree of certainty about causality than adverse reaction, which means any AE caused by a drug.

Life-threatening AE or life-threatening suspected adverse reaction is an AE or suspected adverse reaction that, in the view of either the Investigator or GBT, places the study participant at immediate risk of death. It does not include an AE or suspected adverse reaction that, had it occurred in a more severe form, might have caused death.

An AE or suspected adverse reaction is considered “unexpected” if it is not listed in the Reference Safety Information (RSI) section of the current IB or is not listed at the specificity or severity that has been observed.

An SAE or serious suspected adverse reaction is an AE or suspected adverse reaction that at any dose, in the view of the either the Investigator or GBT, results in any of the following outcomes:

- Death
- A life-threatening AE
- Inpatient hospitalization or prolongation of existing hospitalization

- Persistent or significant incapacity or disability (substantial disruption of the ability to conduct normal life functions)
- A congenital anomaly/birth defect
- Important medical events (IME) that may not result in death, be immediately life-threatening, or require hospitalization may be considered serious when based upon medical judgement, they may jeopardize the study participant and may require medical or surgical intervention to prevent one of the outcomes listed in this definition

NOTE: Hospitalization planned prior to study enrollment (eg, for elective surgeries) are not considered SAEs. Hospitalizations that occur for pre-existing conditions that are scheduled after study enrollment are considered SAEs.

The Investigator will assess each AE for seriousness, severity, and relationship to investigational product.

9.1.2. Severity of Adverse Events

Whenever possible, the severity of all AEs will be graded using the National Cancer Institute (NCI) Common Terminology Criteria for Adverse Events (CTCAE), Version 5.0.

For AEs not adequately addressed in the NCI CTCAE Version 5.0, the following criteria should be used (Table 6).

Table 6: Grading for Adverse Events Not Covered in the NCI CTCAE

Severity	Description
Grade 1 – Mild	Asymptomatic or mild symptoms; clinical or diagnostic observations only; intervention not indicated
Grade 2 – Moderate	Minimal, local or non-invasive intervention indicated; limited age appropriate instrumental activities of daily living (ADL)
Grade 3 – Severe	Medically significant but not immediately life threatening; hospitalization or prolongation of hospitalization indicated; disabling; limiting self-care ADL.
Grade 4 – Life threatening	Life threatening consequences; urgent intervention indicated
Grade 5 – Fatal	Death

NCI CTCAE, National Cancer Institute Common Terminology Criteria for Adverse Events.

To make sure there is no confusion or misunderstanding between the terms “serious” and “severe”, which are not synonymous, the following note of clarification is provided. The term “severe” is often used to describe the intensity (severity) of a specific event (ie, mild, moderate, or severe); the event itself, however, may be of relatively minor medical significance (eg, severe headache). This is not the same as “serious” which is based on the study participant / event outcome or action criteria associated with events that pose a threat to a participant’s life or functioning. Seriousness (not severity) serves as a guide for defining regulatory reporting obligations.

9.1.3. Relationship to Investigational Product

The relationship of an AE to the investigational product should be determined by the Investigator according to the following definitions:

- **NOT RELATED:** Evidence exists that the AE has an etiology other than the study drug and/or the temporal relationship of the AE/SAE to the investigational product administration makes the relationship unlikely. If an SAE is not considered related to study drug, then an alternative explanation should be provided.
- **RELATED:** A temporal relationship exists between the event onset and the administration of the study drug makes a causal relationship possible or probable. It cannot be readily explained by the participant's clinical state or concomitant therapies and may appear, with some degree of certainty, to be related based on the known therapeutic and pharmacologic actions of the drug. Good clinical judgement should be used for determining causal assessment.

9.1.4. Unexpected Adverse Reactions

An AE is "unexpected" if its nature and severity are not consistent with the information about the study drug provided in the RSI in the Voxelotor IB.

9.2. Adverse Event Reporting

9.2.1. General

All AEs will be recorded from the time the study participant signs the ICF until 28 days after the last dose of study drug. After this period, the Investigator should report only SAEs that are assessed as related to study drug until the EOS visit occurs. All SAEs must be reported within 24 hours of SAE awareness on the AE CRF via the electronic data capture (EDC) system. The Investigator is responsible for evaluating all AEs, obtaining supporting documents, and ensuring documentation of the event is complete. Details of each reported AE must include at minimum severity, relationship to study drug, duration and outcome. All (both serious and nonserious) AEs must be followed until they are resolved or stabilized, or until reasonable attempts to determine resolution of the event are exhausted.

Any participant who experiences an AE may be discontinued from study drug at any time at the discretion of the Investigator. The Sponsor and the CRO's Medical Monitors must be notified of the study participant's discontinuation.

9.2.2. Diagnosis Versus Signs and Symptoms

If known, a diagnosis should be recorded on the CRF rather than individual signs and symptoms (eg, record only liver failure or hepatitis rather than jaundice, asterixis, and elevated transaminases). However, if a constellation of signs and/or symptoms cannot be medically characterized as a single diagnosis or syndrome at the time of reporting, each individual event should be recorded separately on the CRF. If a diagnosis is subsequently established, it should be reported as follow-up information.

9.2.3. Abnormal Laboratory Values

Only clinically significant laboratory abnormalities will be recorded on the AE CRF (eg, abnormalities that have clinical sequelae, require study drug dose modification, discontinuation of study drug, more frequent follow-up assessments, further diagnostic investigation). If the clinically significant laboratory abnormality is a sign of a disease or syndrome (eg, ALP and bilirubin above the ULN associated with cholecystitis), only the diagnosis (eg, cholecystitis) needs to be recorded on the CRF.

If the clinically significant laboratory abnormality is not a sign of a disease or syndrome, the abnormality itself should be recorded on the CRF. If the laboratory abnormality can be characterized by a precise clinical term, the clinical term should be recorded. For example, an elevated serum potassium level of 7.0 mEq/L should be recorded as “hyperkalemia.”

Observations of the same clinically significant laboratory abnormality from visit to visit should not be repeatedly recorded on the AE CRF, unless their severity, seriousness, or etiology changes.

9.2.4. Pre-existing Medical Conditions

A pre-existing medical condition is one that is present at the start of the study. Such conditions should be recorded on the Medical History and Baseline Conditions CRF.

If a pre-existing medical condition increases in frequency or severity, or if the character of the condition worsens during the study, the condition should be recorded as an AE or SAE. When recording such events on the AE CRF, it is important to convey the concept that the pre-existing condition has changed by including applicable descriptors (eg, “more frequent headaches”).

9.2.5. Worsening of Sickle Cell Disease

Sickle cell anemia-related AEs that are common complications associated with the study participant’s SCD should not be considered related to voxelotor unless judged by the Investigator to have worsened in severity and/or frequency or changed in nature during the study. Sickle cell anemia-related AEs include: sickle cell anemia with crisis, acute chest syndrome, pneumonia, priapism, and osteonecrosis (Kato, 2018).

9.3. Serious Adverse Events, Serious Adverse Drug Reactions, and Requirements for Immediate Reporting

All SAEs, regardless of causal attribution, occurring on this study will be reported to the Sponsor’s designated CRO’s Drug Safety Department within 24 hours of the Investigator, designee, or site personnel’s knowledge of the event. The SAE will be reported via the EDC system. If the EDC system is not available, paper SAE report forms will be used to report the SAE and faxed or emailed to GBT Pharmacovigilance or CRO designee. The information reported on the paper SAE report form should be entered into the EDC once available.

The Sponsor or designee may request additional source documentation pertaining to the SAE from the investigational site. Follow-up reports must be submitted within 24 hours of awareness and ensure that participant identifier information (eg, name, medical record number) are redacted in the hospital discharge summaries, autopsy reports, and/or death certificates.

Follow-up SAE information must be submitted within 24 hours of awareness as additional information becomes available. All SAEs, regardless of causal attribution, must be followed to resolution, stabilization or until reasonable attempts to determine that resolution of the SAEs are performed.

9.3.1. Reporting Suspected Unexpected Serious Adverse Reactions and Urgent Safety Issues

The Sponsor or its designee is responsible for reporting serious suspected unexpected serious adverse reactions (SUSARs) to regulatory agencies, competent authorities, IECs/IRBs, and Investigators as per local laws and regulations. Fatal and life-threatening SUSARs will be submitted no later than 7 calendar days of the Sponsor's or CRO designee first knowledge of the event and follow-up information submitted within an additional 8 calendar days, or as otherwise required per local laws and regulations. All other SUSARs will be submitted within 15 calendar days of the Sponsor's or CRO designee first knowledge of the event. The Investigator is responsible for notifying the local IECs/IRBs of all SAEs that occur at his or her site, as required by local regulations or IEC/IRB policies, if this responsibility resides with the site.

Investigators are required to report any urgent safety matters to the Sponsor or its designee within 24 hours of awareness. The Sponsor or its designee will inform regulatory authorities, IECs/IRBs, and Investigators, as applicable, of any events (eg, change to the safety profile of voxelotor, major safety findings that may place study participants at risk) that may occur during the clinical trial that do not fall within the definition of a SUSAR but may adversely affect the safety of study participants.

9.4. Reporting Pregnancy

If a participant becomes pregnant while taking study drug, the study drug will be immediately discontinued, and the pregnancy must be reported to the Sponsor or designated Drug Safety CRO within 24 hours of awareness. The Investigator will discuss the risks and concerns of investigational agent exposure to a developing fetus and counsel the participant and/or pregnant partner (or ensure such counseling is provided).

Reported pregnancy of a participant or a participant's partner while participating in this study will be monitored for the full duration of the pregnancy, and/or followed through a definitive outcome (ie, birth, or spontaneous or elective abortion). Pregnancies in partners of male study participants will similarly be monitored for the full duration of the pregnancy and/or followed through a definitive outcome (ie, birth, or spontaneous or elective abortion).

An uncomplicated pregnancy will not be considered an AE or SAE. Pregnancy complications such as spontaneous abortion/miscarriage and congenital anomalies are considered SAEs and must be reported as described in Section 9.3. Note: an elective abortion is not considered an SAE. Pregnancy and pregnancy outcomes must be reported on a Pregnancy Notification or Pregnancy Outcome Form, respectively, and sent to the Sponsor or designated Drug Safety CRO within 24 hours of the Investigator, designee, or site personnel learning of the pregnancy or pregnancy outcome.

The child born to a female participant or participant's partner exposed to study drug will be followed for 3 months after delivery. The outcome of any pregnancy and the presence or absence

of any congenital abnormality will be recorded in the Pregnancy Outcome Form and reported to the Sponsor or designated Drug Safety CRO. Any congenital abnormalities in the offspring will be reported as an SAE and must be reported as described in Section 9.3.

Information regarding pregnancy testing (including definition of females of child-bearing potential) is provided in Section 6. Highly effective means of contraception are listed in Section 6.4.

9.5. Reporting Overdose

If a participant takes more than the protocol-defined dose in a day and experiences a drug-related AE, this will be reported as an overdose and a protocol deviation. However, if the participant did not experience any AEs, this will only be reported as a protocol deviation.

The Investigator will discuss the risks and concerns of investigational agent exposure with the participant. Participants are to be instructed to contact their study site immediately if an overdose of study drug is suspected. A suspected overdose with AEs should be reported to the Sponsor's designated CRO's Drug Safety Department within 24 hours of the Investigator, designee, or site personnel's knowledge of the event. An overdose with AEs must be followed until the adverse effects are resolved or stabilized, or until reasonable attempts to determine resolution of the event are exhausted.

9.6. Safety Monitoring Committee

See Section 3.4 for information regarding the SMC.

10. DATA ANALYSIS AND STATISTICAL PLANS

10.1. Endpoints

10.1.1. Primary Endpoint

The primary endpoints are:

- TEAEs and SAEs

10.1.2. Secondary Endpoints

The secondary endpoints are:

- Change in Hb and clinical measures of hemolysis (unconjugated bilirubin, % reticulocyte, absolute reticulocyte, and LDH) from Baseline
- Proportion of participants with an Hb increase > 1 g/dL compared to Baseline
- Incidence rate of VOCs

10.1.3. Exploratory Endpoints

The exploratory endpoints are:

- P50 and P20 at 8 hours and 24 hours postdose
- PK of voxelotor as assessed by population PK analysis using nonlinear mixed-effect modeling
- % Hb occupancy at 8 hours and 24 hours postdose
- CGI-C
- PGI-C

10.2. Determination of Sample Size

As this is an exploratory study to provide descriptive information on the tolerability, safety, and efficacy of voxelotor at dose levels > 1500 mg daily, the sample size chosen was based on previous experience in exploratory studies to support the assessment of a MTD based on descriptive summaries of safety and PK data. The sample size of up to 40 participants takes into account the differential tolerance in participants, some potentially tolerating 3000 mg daily, while others only tolerating lower dose levels. An effort will be made to enroll a number of subjects sufficient to ensure that at least 6 participants are treated at the study level MTD.

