1.5.1. Study Rationale

In the pivotal Phase 3 Study GBT440-031, voxelotor was shown to have a dose-dependent (1500 mg > 900 mg orally daily), and clinically meaningful increase in Hb, as well as concurrent reductions in clinical measures of hemolysis. Study GBT440-029, is designed to assess tolerability, safety, and PD of voxelotor dose levels higher than 1500 mg daily (the maximum dose in the pivotal Phase 3 study) and to compare these results to the 1500 mg dose. The rationale for this study is based on an exposure-response analysis from the pivotal Study GBT440-031, which showed a linear relationship between whole blood voxelotor and %Hb occupancy and efficacy as measured by improvement in Hb (see Figure 1 below) and hemolysis markers. The 1500 mg dose led to a mean Hb occupancy of 29% and led to a mean Hb increase of 1.1 g/dL. At 3000 mg of voxelotor, assuming a linear relationship, the mean Hb occupancy is projected to be 49.3% with a Hb increase of 2.04 g/dL. Furthermore, no dose level has been associated with exposure-related concerning safety signals, and a maximum tolerated dose (MTD) has not been defined. Treatment-related AEs were mostly grade 1/grade 2 gastrointestinal events. Given the predicted improved efficacy of higher doses, and lack of dose-limiting safety concerns, this study will investigate the potential for a greater benefit/risk for higher doses in patients with SCD.

In this study, baseline response will be characterized in participants receiving a 3-week treatment regimen with voxelotor 1500 mg and compared, within and across participants, to the response with the highest dose level tolerated at steady state. Dose escalation will be done in 3-week increments to assess tolerability at the escalated dose.

Figure 1: Relationships Between Change from Baseline in Hemoglobin at Week 24 and Percent Hemoglobin Occupancy

pkpd-wk24-hgb-20190508.pdf

C_{min} , minimum plasma concentration at steady state; CFB, change from baseline; Hb, hemoglobin.

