3.2. Study Design

This is an open-label, sequential period, within-participant dose escalation study. Up to 40 participants with SCD (HbSS or HbSB⁰) who are 18 to $<$ 60 years of age, inclusive, will be enrolled.

Study participants will undergo up to four periods of voxelotor administration at progressively higher dose levels from 1500 mg until either a MTD or 3000 mg daily dose is reached, whichever occurs first ([Figure 2](#)):

- Period 1: 1500 mg per day: 1500 mg once daily (3×500 mg tablets) for 3 weeks (± 3 days)
- Period 2: 2000 mg per day: 1000 mg (2×500 mg) BID for 3 weeks (± 3 days)
- Period 3: 2500 mg per day: 1500 mg (3×500 mg) in morning and 1000 mg (2×500 mg) in evening daily for 3 weeks (± 3 days)
- Period 4: 3000 mg per day: 1500 mg (3×500 mg) BID for 3 weeks (± 3 days)
- Observation Period: MTD or 3000 mg daily for 24 weeks
- Safety Follow-up Period: from day of last dose to 28 days postdose.

[figure not shown]
If at any time a dose level $>$ 1500 mg is not tolerated by a participant in the dose escalation period, the dose may be reduced to a previous level for the participant, which will then be administered for 24 additional consecutive weeks as an observation period. Dose modifications are allowed during the observation period in consultation with the Sponsor's Medical Monitor ([Appendix C](#)).

If 1500 mg daily is the MTD for a participant, then the participant may enter the observation period and continue to receive 1500 mg, for up to 24 weeks or until they are able to roll over into the open-label extension or receive commercial voxelotor, where available. If the participant discontinues early from the study, the participant will undergo an End of Study (EOS) visit approximately 28 days after the last dose and will not be eligible for the open-label extension study.

The safety of study participants will be closely monitored by the study team. In addition, a Safety Monitoring Committee (SMC) will review safety, tolerability, and available PK and PD data at regular intervals (Section [3.4](#)). Blood draws for PK and PD (including Hb and hemolysis markers), routine chemistry and hematology laboratory tests, and 12-lead ECGs in triplicate will be obtained periodically, as listed in the Schedule of Assessments ([Appendix A](#), [Appendix B](#)).

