10.4. Data Analysis

Data will be presented by maximum dose level.

A TEAE, defined as an event that occurs on or after Day 1 of study drug or the worsening of a pre-existing condition on or after Day 1 of study drug, will be classified according to the Medical Dictionary for Regulatory Activities (MedDRA). The incidence of TEAEs and relatedness to study drug, as assessed by the Investigator, will be summarized descriptively by maximum dose level tolerated.

Clinical laboratory tests, ECGs, and vital signs over time will be summarized by maximum dose level tolerated using descriptive statistics. Change from baseline in ECG intervals will be evaluated using descriptive statistics. If an effect on mean change from baseline in QTc interval exceeding 10 msec is observed, concentration-QTc analysis may be explored. Results from the diagnostic interpretation will be summarized by maximum dose tolerated.

An Hb responder endpoint, defined as an increase in Hb of > 1 g/dL compared to Baseline, will be summarized. Additionally, change from baseline in hemoglobin and clinical measures of hemolysis (unconjugated bilirubin, % reticulocyte, absolute reticulocyte, and LDH) will be summarized by maximum dose level tolerated using descriptive statistics.

The incidence of VOCs will be summarized by maximum dose tolerated.

The CGI-C and PGI-C will be summarized by maximum dose level tolerated.

Population PK analysis using nonlinear mixed-effect modeling will be performed to characterize voxelotor PK in plasma, and whole blood.

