^f If positive urine test, serum pregnancy test will be done to confirm result.

^g Samples for hemoximetry will be obtained predose (within 30 minutes prior to dosing) at the investigational site.

^h Visits should take place in the morning. Participants are instructed to hold study drug until a predose blood sample for PK is obtained at the investigational site.

ⁱ During the observation period, the participant will receive their maximum tolerated dose or 3000 mg daily.

^j During the observation period, blood samples for PK will be obtained predose (within 30 minutes prior to dosing) at the investigational site.

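### Adverse events are grouped only by the highest dose each participant tolerated, so no planned table gives the tolerability of 2000, 2500 or 3000 mg/day among those who started it

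*Combined protocol and SAP*

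**What the plan says.** Section 2.1 makes tolerability and safety at 2000 to 3000 mg/day the primary objective. Section 10.2 (repeated in the synopsis) states that "the sample size chosen was based on previous experience in exploratory studies to support the assessment of a MTD based on descriptive summaries"; these summaries cover the safety and PK results. It sets a ceiling of 40 and aims to enrol a number "sufficient to ensure that at least 6 participants are treated at the study level MTD". The study-level term appears only in that sentence and its synopsis copy, and is not defined.

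The design itself assigns an MTD to each person. Section 3.2 has "If 1500 mg daily is the MTD for a participant", and Appendix B says that in the observation period "the participant will receive their maximum tolerated dose or 3000 mg daily".

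Section 10.4 opens with "Data will be presented by maximum dose level". It then specifies that treatment-emergent events, laboratory tests, ECGs and vital signs are summarised by the highest dose level tolerated. No endpoint in section 10.1 and no other analysis in section 10.4 counts dose-limiting events by the dose being taken.

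Section 3.7.2 has one numerical rule at dose level: three or more participants with similar, related serious events pause escalation for Safety Monitoring Committee review. The committee may also stop escalation on the totality of the data.

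**The concern.** In a within-participant escalation, the highest dose tolerated is known only after the tolerability result is in. Grouping adverse events by it sorts participants by the outcome being measured. Events that make a dose intolerable move to the column of the dose below, and the top column keeps only those without such an event.

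A second distortion is timing. A treatment-emergent event is any event on or after Day 1, so events during earlier, lower-dose periods also fall in the column of the final dose. A participant who reaches 3000 mg spends 3 weeks at each of 1500, 2000 and 2500 mg, which is 9 of 36 treatment weeks (12 in escalation plus 24 in observation), or 25%.

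At stake is the primary question: of those who start a given dose above 1500 mg/day, how many cannot stay on it? The MTD assessment that section 10.2 cites in support of the sample size needs the same figure.

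**Working it through.** **The plan's figures.** Neither 40 nor 6 can be reproduced. Section 10.2 gives no target rate, precision or decision rule. For a descriptive study this is a missing derivation and not a wrong number.

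**What the planned grouping shows.** The documents give no tolerance rates, so the counts here are assumed for illustration only. Take 40 participants who all start 2000 mg, with individual MTDs of 1500, 2000, 2500 and 3000 mg in 4, 10, 12 and 14. Everyone below 3000 mg stopped there because of a limiting event at the next dose.

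- Starters: 2000 mg = 40; 2500 mg = 40 − 4 = 36; 3000 mg = 36 − 10 = 26.
- Limiting events at each dose: 4, 10 and 12.

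| Column | Limiting events over starters (exact 95% limits) | Grouped by highest dose tolerated | Grouped by highest dose received |
|---|---|---|---|
| 1500 mg | not applicable | 4/4 | no participants |
| 2000 mg | 4/40 = 10.0% (2.8 to 23.7%) | 10/10 | 4/4 |
| 2500 mg | 10/36 = 27.8% (14.2 to 45.2%) | 12/12 | 10/10 |
| 3000 mg | 12/26 = 46.2% (26.6 to 66.6%) | 0/14 | 12/26 |

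Grouped by highest dose tolerated, the true rise from 10% to 46% becomes 100% in every lower column and 0% at 3000 mg. The last column covers the looser opening sentence of section 10.4, which omits the word tolerated. On that reading only the 3000 mg figure is right, and 2000 and 2500 mg still show 100%. The contrast is this stark because the example allows no other reason for stopping, but the direction follows from the grouping.

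**Consequence for an MTD.** From the same 40 participants:
- most frequent individual MTD: 3000 mg (14 participants);
- median individual MTD: 2500 mg (4 + 10 = 14 fall below it, and 14 + 12 = 26 are at or below it);
- highest dose with under 33% limiting events among starters: 2500 mg;
- highest dose with at most 20% among starters: 2000 mg.

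The plan names none of these rules, and its tables would not supply the starter-based rates.

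**Who counts toward the 6.** Under section 3.2, participants pass through lower doses on the way up. Being treated at a dose could therefore mean having started it or having it as one's own MTD. Assume step tolerances of 90%, 80% and 70% at 2000, 2500 and 3000 mg. The share starting 2500 mg is 0.9. The share with 2500 mg as own MTD is 0.9 × 0.8 × 0.3 = 0.216.

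| Enrolled | Expected to start 2500 mg | Expected own MTD 2500 mg | Probability of at least 6 with own MTD 2500 mg |
|---|---|---|---|
| 20 | 18.0 | 4.3 | 25% |
| 28 | 25.2 | 6.0 | 58% |
| 40 | 36.0 | 8.6 | 89% |

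The two readings give different counts at every size, but at the ceiling of 40 both would probably reach 6.

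**Precision of 6.** With 0 events in 6, the exact two-sided 95% upper limit is 1 − 0.025^(1/6) = 45.9%.

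**The case against.** The study is exploratory, and section 10.2 says openly that the MTD will be judged from descriptive summaries. A study-level MTD is neither an objective nor an endpoint, and the 6 is a best-effort aim. An undefined term in such a sentence is, on its own, missing detail. All of this stands, and the absence of a power calculation is no fault here. It does not rescue the grouping, because a descriptive judgement needs summaries that describe each dose.

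A reader might infer more than the documents support:
- *That the target of 6 will be missed.* This needs a small enrolment. The plan allows up to 40 and says enrolment should be sufficient to reach 6.
- *That the plan treats the MTD only as an individual quantity outside section 10.2.* It does not. Section 1.5.1 says "a maximum tolerated dose (MTD) has not been defined", and section 1.5.2 also uses the term for the compound.
- *That nothing operates at dose level.* Section 3.7.2 does, and section 3.4 leaves the committee's scope, responsibilities and frequency to a charter outside the documents. But the pause rule has no denominator and declares no MTD, and nothing says the charter defines one.

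**Conclusion.** The concern holds as a fault in the analysis. Followed as written, section 10.4 cannot give the proportion of starters who fail 2000, 2500 or 3000 mg/day, and it can make the highest dose look the best tolerated. This follows from the grouping rule and needs no assumption. The size shown, 0/14 against a true 12/26 at 3000 mg, rests on assumed counts and on dose failure being the only reason for not reaching 3000 mg.

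The undefined study-level MTD is secondary. It matters because section 10.2 refers to an assessment for which the tables provide no basis. The documents do not show that the sample size is wrong, that the aim of 6 is out of reach, or that participants lack safety rules. The change should be made before the data are reviewed.

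**What to change.** 1. **Section 10.4, tolerability table.** For 2000, 2500 and 3000 mg/day in the dose escalation period, use participants who started the dose as the denominator. The numerator is those who, on that dose, met a section 3.7.3.1 criterion or had a reduction, hold or discontinuation for a study-drug-related adverse event. The second part is needed because the section 3.7.3.1 list is open-ended and Appendix C allows reduction for related Grade 2 events that need not meet a listed criterion. Show exact 95% limits.
2. **Section 10.4, adverse events.** Also tabulate treatment-emergent events by dose at onset. The present grouping can stay as a supplement.
3. **Section 10.2.** State that the 6 are participants who started the dose and either completed its 3-week period or had an event counted in item 1.
4. **Study-level MTD, only if one is to be reported.** Derive it from the item 1 table, with a limit the sponsor fixes before reviewing the data. Report two cases separately: MTD not reached up to 3000 mg (3000 mg within the limit), and no dose above 1500 mg within the limit. No limit or dose is proposed here.

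The cost is one extra tolerability table, a second layout of the adverse event table, and wording in two sections. No participants, visits or data are added: adverse events and treatment administration are already recorded (sections 9.2.1 and 11.2). The downside is that the sponsor must commit to a limit in advance if it wants to name a study-level MTD.
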